#### **6.7.1. Reporting and Follow-up of Overdose**

Symptomatic overdose is an AESI as defined in [Section 8.3.6](#). If a participant should experience symptomatic overdose, the investigator will report the symptomatic overdose to the study medical monitor and complete the required information in the electronic data capture (EDC)

system within 24 hours of study staff becoming aware of the overdose. Follow-up on the participant's condition will be conducted by the investigator and study staff.

## **6.8. Prior and Concomitant Therapy**

Any medication or vaccine, including over-the-counter or prescription medicines, vitamins, and/or herbal supplements a participant is taking will be monitored at all study visits from Screening until the end of the study and documented on the appropriate electronic case report form (eCRF), including start/stop dates, dose, route of administration, and indication.

### **6.8.1. Prior Medication**

At the time of providing signed informed consent, participants will be asked about medication use during the previous 30 days, including prescription and nonprescription medications, herbal medications, vitamins, and minerals. Any prohibited medication and restricted food items must be discontinued for  $\geq 14$  days before screening may proceed.

### **6.8.2. Background HFpEF Medication**

As results of clinical trials to date in HFpEF have generally been neutral, management of the condition is primarily focused on associated symptoms (eg, edema) and/or conditions (eg, hypertension and atrial fibrillation). Background medications for HFpEF and related conditions and symptoms (eg, antihypertensives and mineralocorticoid antagonists) are allowed during the study unless specifically excluded by eligibility criteria. The treatment should be well tolerated for at least 2 weeks prior to screening and should generally be maintained through the EOS visit. In this context, investigators are encouraged not to change background medications (including dose) from Day 1 to Week 34; however, investigators should manage participants appropriately using their clinical judgment. Any change in medications must be entered into the eCRF with the rationale for the change.

### **6.8.3. Prohibited Medication**

Medications that are prohibited during the study are outlined in [Section 10.2](#). Prior or concomitant treatment with cardiotoxic agents, such as doxorubicin or similar, is prohibited.

The study medical monitor should be contacted for any questions regarding prior or concomitant medications.

### **6.8.4. COVID-19 Vaccine Considerations**

Locally authorized or approved COVID-19 vaccines that are NOT live are allowed and should be handled in the same manner as other vaccines. Administration may occur during the study, including during the administration of mavacamten study treatment and after the last administration of mavacamten study treatment.

## **7. DISCONTINUATION OF STUDY DRUG AND PARTICIPANT DISCONTINUATION/WITHDRAWAL**

### **7.1. Discontinuation of Study Drug**

Temporary treatment discontinuation:

- Will be implemented when a predefined safety threshold [REDACTED] has been met.
- May be considered by the investigator in the case of an AE/SAE or for another reason.

As a general rule, any discontinuation of study drug should be initially considered temporary unless permanent treatment discontinuation is mandated.

In rare instances, it may be necessary for a participant to permanently discontinue study drug. If study drug is permanently discontinued, the participant will be encouraged to remain in the study to be evaluated for safety and study endpoints as appropriate through the EOS visit. See the Schedule of Study Procedures ([Table 1](#)) for data to be collected at the time of discontinuation of study drug and follow-up and for any further evaluations that need to be completed.

#### **7.1.1. Liver Chemistry Stopping Criteria**

Participants with abnormal hepatic laboratory values (eg, alkaline phosphatase [ALP], AST, ALT, total bilirubin [TBL], or international normalized ratio [INR]) or signs/symptoms of hepatitis may meet the criteria for withholding of study drug or other protocol-required therapies. Withholding is either permanent or conditional depending on the clinical circumstances discussed below as specified in the United States (US) Food and Drug Administration (FDA) Guidance for Industry–Drug Induced Liver Injury: Premarketing Clinical Evaluation, July 2009.

##### **7.1.1.1. Criteria for Permanent Withholding of Mavacamten Due to Potential Hepatotoxicity**

Mavacamten should be discontinued permanently and the participant should be followed according to the recommendations in [Section 10.5](#) for possible drug-induced liver injury (DILI), if all the criteria below are met:

- $TBL > 2 \times ULN$  or  $INR > 1.5$ .
- AND increased AST or ALT, if the baseline value was  $<ULN$  and AST or ALT elevation is  $> 3 \times ULN$ .
- AND no other cause for the combination of laboratory abnormalities is immediately apparent. Important potential causes for abnormal AST/ALT or TBL values include, but are not limited to, the following:
  - Obstructive gall bladder or bile duct disease.
  - Viral or alcoholic hepatitis (eg, hepatitis A/B/C/D/E, Epstein-Barr virus, cytomegalovirus, herpes simplex virus, varicella).
  - Hypoxic or ischemic hepatopathy or congestive hepatopathy in association with significant right sided heart failure.

CONFIDENTIAL

Approved v2.0

- Concomitant administration of other hepatotoxins, including drugs that inhibit bilirubin glucuronidation (eg, indinavir, atazanavir, irinotecan) or herbal or dietary supplements.
- Heritable disorders causing impaired glucuronidation (eg, Gilbert syndrome);  $\alpha$ -1 antitrypsin deficiency.
- Autoimmune hepatitis.
- Nonalcoholic steatohepatitis (NASH) or other fatty liver disease.

If an alternative cause for hepatotoxicity is identified, or less stringent conditions develop than what is noted above, the investigator will determine whether study drug and other protocol-required therapies should be permanently or temporarily discontinued based on the participant population and/or the severity of the hepatotoxicity or event, as deemed appropriate for the safety of the participant.

#### **7.1.1.2. Criteria for Conditional Withholding of Mavacamten Due to Potential Hepatotoxicity**

For participants who do not meet the criteria for permanent withholding of study medication outlined in [Section 7.1.1.1](#), mavacamten should be withheld if ANY of the following criteria are met, and the participant should be evaluated for DILI:

- AST or ALT  $> 8 \times$  ULN at any time.
- AST or ALT  $> 5 \times$  ULN and  $< 8 \times$  ULN for  $\geq 2$  weeks.
- AST or ALT  $> 5 \times$  ULN and  $< 8 \times$  ULN and unable to adhere to enhanced monitoring schedule.
- ALT or AST  $> 3 \times$  ULN and (TBL  $> 2 \times$  ULN or INR  $> 1.5$ ).
- ALT or AST  $> 3 \times$  ULN and clinical signs or symptoms that are, in the opinion of the investigator, consistent with hepatitis (such as right upper quadrant pain/tenderness, fever, nausea, vomiting, jaundice, rash, or eosinophilia  $> 5\%$ ).
- TBL  $> 3 \times$  ULN at any time.
- ALP  $> 8 \times$  ULN at any time.

[figure not shown]
Mavacamten should be withheld pending an investigation into alternative causes of DILI. If mavacamten is withheld, the participant should be followed according to recommendations for possible DILI ([Section 10.5](#)). Rechallenge may be considered if an alternative cause, such as acute hepatitis B infection, is discovered and the laboratory abnormalities resolve to normal or baseline ([Section 7.1.1.3](#)).

#### **7.1.1.3. Criteria for Rechallenge of Mavacamten After Potential Hepatotoxicity**

The decision to rechallenge a participant should be discussed and unanimously agreed upon by the investigator, the study co-coordinating investigators, and MyoKardia or their designee.

If signs or symptoms recur with rechallenge, then mavacamten will be permanently discontinued. Participants who clearly meet the criteria for permanent discontinuation (as described in [Section 7.1.1.1](#)) should never be rechallenged.

CONFIDENTIAL

Approved v2.0

## 7.2. Participant Discontinuation/Withdrawal from the Study

A participant may withdraw from the study at any time at his/her own request or may be withdrawn at any time at the discretion of the investigator or MyoKardia or their designee for safety, behavioral, or compliance reasons. This is expected to be uncommon.

At the time of discontinuing from the study, if possible, an early drug discontinuation visit should be conducted, as shown in the Schedule of Study Procedures ([Table 1](#)). See the Schedule of Study Procedures for data to be collected at the time of study discontinuation.

The participant will be permanently discontinued both from the study drug and from the study at that time.

If the participant withdraws consent for disclosure of future information, MyoKardia or their designee may retain and continue to use any data collected before such a withdrawal of consent.

If a participant withdraws from the study, he/she may request destruction of any samples taken and not tested, and the investigator must document this in the site study records.

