### 5.3. Lifestyle Considerations

The following restrictions apply for the specified times during the study period. If a participant does not comply with these restrictions or tests positive in any laboratory tests (eg, drug, alcohol, pregnancy), he/she may be excluded or withdrawn from the study.

- Starting 72 hours prior to the first dose of study drug until the final follow-up visit, participants should not engage in unaccustomed intensive exercise except during protocol-specified exercise tests.
- Starting at Screening, participants will be required to abstain from blood or plasma donation until 3 months after the final study visit.
- Starting on Day 1 until the final follow-up visit, participants will be asked to abstain from grapefruit or grapefruit juice, Seville oranges, and quinine (eg, tonic water).
- Starting at the time of signing informed consent, participants must abstain from taking biotin and biotin-containing supplements/multivitamins.

Contraception requirements are discussed in the inclusion criteria in [Section 5.1](#).

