#### **8.3.1. Time Period and Frequency for Collecting AE and SAE Information**

All AEs, including SAEs, will be collected from the signing of the informed consent form (ICF) until 56 days after the last dose of study drug ([Table 1](#)).

Medical occurrences that begin before the start of study drug but after obtaining informed consent will be recorded as pretreatment adverse events (PTAEs), as detailed in [Section 10.4](#).

All SAEs/AESIs will be recorded and reported to MyoKardia or their designee immediately and under no circumstance should this exceed 24 hours, as indicated in [Section 10.4](#). The investigator will submit any updated SAE data to MyoKardia or their designee within 24 hours of it being available.

Investigators are not obligated to actively seek information on AEs or SAEs after conclusion of the study participation. However, if the investigator learns of any SAE, including a death, at any time after a participant has been discharged from the study, and he/she considers the event to be reasonably related to the study drug or study participation, the investigator must promptly notify MyoKardia or their designee (via paper SAE form).

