- Any post-study pregnancy-related SAE considered reasonably related to the study drug by the investigator will be reported to MyoKardia or their designee, as described in [Section 8.3.4](#). While the investigator is not obligated to actively seek this

CONFIDENTIAL

Approved v2.0

information in former study participants or pregnant female partners of male participants, he/she may learn of an SAE through spontaneous reporting.

- Any female participant who becomes pregnant while participating in the study will discontinue study drug.

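### Discretionary withdrawal from the whole study (Sections 7.2 and 5.3) drops the EOS visit and puts the 56-day safety follow-up at risk, in conflict with Sections 7.1, 4.1, 8.3.1 and 8.3.5

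*Combined protocol and SAP*

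**What the plan says.** Two sets of provisions bear on who stays under observation after treatment ends.

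**Provisions that end observation**
- Section 7.2: a participant "may be withdrawn at any time at the discretion of the investigator or MyoKardia or their designee for safety, behavioral, or compliance reasons". The consequence is stated without qualification: "The participant will be permanently discontinued both from the study drug and from the study at that time". On the last visit, "if possible, an early drug discontinuation visit should be conducted". On frequency: "This is expected to be uncommon".
- Section 5.3: a participant who breaks a lifestyle restriction, or who "tests positive in any laboratory tests (eg, drug, alcohol, pregnancy), he/she may be excluded or withdrawn from the study".
- Table 1 footnote f: the Early Discontinuation Visit serves both drug discontinuation and study withdrawal, but the EOS visit is retained only for the first.
- Section 8.3.1: investigators need not look actively for AEs or SAEs after participation ends. Once a participant is discharged, only SAEs judged reasonably related need to be notified.

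**Provisions that continue observation**
- Section 7.1: "If study drug is permanently discontinued, the participant will be encouraged to remain in the study", with evaluation through EOS.
- Section 4.1: participants who stop drug early attend a visit within 14 days and also the EOS visit.
- Section 8.3.1: AEs and SAEs are collected "until 56 days after the last dose of study drug". Sections 8.3.4 and 10.4.2.3 require all SAEs in that period to be reported regardless of causality, and Section 9.4.4 makes it the focus of the safety analysis.
- Section 8.3.5: "Any female participant who becomes pregnant while participating in the study will discontinue study drug", and the outcome is followed to 6 months after birth.

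**The concern.** Safety and tolerability is the first-listed primary objective of a single-arm study in about 35 participants. Section 7.1 separates stopping drug from leaving the study. Section 7.2 lets the investigator or sponsor end both at once on grounds that include safety, and gives no criterion for choosing between the two routes. Two sites facing a similar event could therefore keep one participant in follow-up and release the other.

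Withdrawal for safety is informative by its own stated reason, because it ends scheduled observation in participants chosen for how they fared on drug. Section 9.4.4.1 takes the safety population as the denominator for AE percentages. Unless the SAP says otherwise, a new event that the site never learns of after withdrawal would be counted as no event. No handling of such withdrawals is visible in Section 9, parts of which are blacked out. Section 9.4 leaves detail to the SAP, which is not in the supplied text.

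**Working it through.** **1. The plan's own figure.** The post-treatment follow-up is 8 weeks (Section 4.1): 8 × 7 = 56 days. Week 26 to Week 34 is (34 − 26) × 7 = 56 days. Both agree with the 56-day window in Section 8.3.1. There is no sample-size calculation to reproduce (Section 9.2) and no hypothesis test (Section 9.1).

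**2. The same participant under the two routes**

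| | Drug stopped (7.1, 4.1) | Withdrawn from study (7.2, 5.3) |
|---|---|---|
| Early visit | Required, within 14 days | Asked for, if possible |
| EOS visit | Kept | Not provided for (footnote f) |
| AE/SAE window to day 56 | Applies | Applies with no stated exception, but the duty to seek events ends with participation (8.3.1) |
| Unrelated SAE at, say, day 30 | Reportable | Reportable under 8.3.4 and 10.4.2.3; not among those to be notified after discharge under 8.3.1 |

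The last two rows are a conflict between sections. Only the EOS row is a definite loss.

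**3. Scheduled contact left in the window.** Assume the last dose is taken on the day drug is stopped. If the early visit falls at the 14-day limit of Section 4.1, 56 − 14 = 42 days (42/56 = 75%) have no scheduled contact. If the visit does not take place, all 56 days have none.

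**4. Effect on an event proportion.** Take x participants with the event among 35, and k withdrawn without it whose later status is unknown. The true proportion lies between x/35 and (x + k)/35, a width of k/35. The values of k are assumptions.

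| k | Width (percentage points) | Range if x = 2 |
|---|---|---|
| 1 | 2.9 | 5.7% to 8.6% |
| 2 | 5.7 | 5.7% to 11.4% |
| 3 | 8.6 | 5.7% to 14.3% |
| 5 | 14.3 | 5.7% to 20.0% |

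**5. Effect on a zero count.** The one-sided 95% exact upper limit with no events is 1 − 0.05^(1/n). It is 8.2% for n = 35 and 9.5% for n = 30 (five not followed). The loss of precision is small. Bias from selective loss matters more.

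**6. How likely the problem is to arise.** The expected number of withdrawals is 35p, and the chance of at least one is 1 − (1 − p)^35. For an assumed p of 3%, 5% or 10%, the expected number is 1.05, 1.75 or 3.5, and the chance is 66%, 83% or 97%.

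**The case against.** The strongest reply is that these sections leave less unobserved than a quick reading suggests. Most of that stands.

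- **The 56-day window.** A reader might infer that the window is lost by rule. It is not: Sections 8.3.1, 8.3.4 and 10.4.2.3 contain no exception for withdrawn participants. What remains is that Section 8.3.1 also removes the duty to seek events, so the window depends on which sentence a site follows.
- **Recovery from known events.** A reader might infer that this is lost too. Sections 8.3.3, 10.4.2.2 and 10.4.2.4 keep known events under follow-up, and Section 10.5 requires at least 4 weeks of close observation after discontinuation for potential liver injury. The event that prompted withdrawal would normally be recorded already. The exposure is to new, later events.
- **Pregnancy.** Outcomes are tracked under Sections 8.3.5 and 10.4.4.2 whichever route is taken, and all participants are at least 50. The mismatch with Section 5.3 is one of wording.
- **Week 34 biomarkers.** A reader might infer that each withdrawal weakens the case in Section 4.2 for omitting a placebo group. That case concerns decreases seen at Week 26 that reverse by Week 34, so it is touched only where a Week 26 value exists.
- **LVEF.** The stopping thresholds are blacked out, so divergence between sites after a fall in LVEF cannot be judged.
- **Discretion.** Withdrawal is optional and expected to be uncommon. The wording in Section 5.3 also covers exclusion before dosing, and Section 7.1 itself only encourages participants to stay. Keeping some discretion is a legitimate design choice.

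None of this restores the EOS visit after withdrawal under Section 7.2, or settles whether sites must look for new events up to day 56.

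**Conclusion.** The point holds as a conflict over who stays under observation. After investigator- or sponsor-initiated withdrawal, the EOS visit is lost and active collection to last dose + 56 days is at risk, on grounds tied to a primary safety endpoint. The size is 2.9 percentage points (1/35) of worst-case width for each participant whose later status is unknown. It scales with a number of withdrawals that the protocol does not state and expects to be small. The rates of 3% to 10% used above are assumptions that show the range, not forecasts.

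The documents do not support the stronger claim that the safety window disappears for the participants who tolerate the drug worst. No significance level, power or sample-size figure is affected. This is a cheap improvement, not a flaw that invalidates the design.

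**What to change.** Reconcile Sections 7.2, 5.3, 7.1, 4.1, 8.3.1 and 8.3.5 with Table 1 footnote f. The change concerns observation only and should not prescribe when study drug is stopped.

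- In Section 7.2, with a cross-reference from Section 5.3, state that after withdrawal initiated by the investigator or sponsor, active AE and SAE collection continues to last dose + 56 days and an EOS visit or contact is completed, unless the participant withdraws consent or is lost to follow-up.
- In Section 8.3.1, make clear that the release from actively seeking events does not begin before day 56 for these participants.
- Extend footnote f to them. Also settle its EOS timing, about 8 weeks after the Early Discontinuation Visit, against Week 34 in Section 4.1.
- Align the pregnancy wording in Section 5.3 with Section 8.3.5.
- In the SAP, report such withdrawals by reason, with the completeness of the 56-day follow-up.

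The cost is a few sentences of protocol text, one added summary, and a little more site effort for a few participants.

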## 7.3. Lost to Follow-up

A participant will be considered lost to follow-up if he/she repeatedly fails to return for scheduled visits and is unable to be contacted by the study site.

The following actions must be taken if a participant fails to return to the clinic for a required study visit:

- The site must attempt to contact the participant and reschedule the missed visit as soon as possible and counsel the participant on the importance of maintaining the assigned visit schedule and ascertain whether or not the participant wishes to and/or should continue in the study.
- Before a participant is deemed lost to follow-up, the investigator or designee must make every effort to regain contact with the participant (where possible, at minimum 3 telephone calls and, if necessary, a certified letter to the participant's last known mailing address or local equivalent methods). These contact attempts should be documented in the participant's medical record.
- Should the participant continue to be unreachable, he/she will be considered to have withdrawn from the study.
- Site personnel, or an independent third party, will attempt to collect the vital status of the participant within legal and ethical boundaries for all enrolled participants, including those who did not receive study drug. Public sources may be searched for

CONFIDENTIAL

Approved v2.0

vital status information. If vital status is determined as deceased, this will be documented and the participant will not be considered lost to follow-up. Sponsor personnel will not be involved in any attempt to collect vital status information.

Discontinuation of specific sites or of the study as a whole are handled as part of Appendix 1 in [Section 10.1](#).

## **8. STUDY ASSESSMENTS AND PROCEDURES**

Study procedures and their timing are summarized in the Schedule of Study Procedures ([Table 1](#)). Protocol waivers or exemptions are not allowed.

Immediate safety concerns should be discussed with MyoKardia or their designee immediately upon occurrence or awareness to determine if the participant should continue or discontinue study drug.

Adherence to the study design requirements, including those specified in the Schedule of Study Procedures, is essential and required for study conduct.

Prescreening evaluations are optional and may be performed to assess chronic values of cardiac biomarkers if no historical values of chronic NT-proBNP or cardiac troponins are available. All screening evaluations must be completed and reviewed to confirm that potential participants meet all eligibility criteria. The investigator will maintain a screening log to record details of all participants screened and to confirm eligibility or record reasons for screening failure, as applicable.

Repeat or unscheduled samples may be taken for safety reasons or for technical issues with the samples.

At the investigator's discretion or per the request of MyoKardia or their designee, unscheduled visits may be conducted for reasons including, but not limited to, assessment of AEs, new or worsening symptoms, physical examinations, vital signs, laboratory tests, ECGs, [REDACTED]. ECGs [REDACTED] conducted at unscheduled visits will be sent to the respective core laboratory for central reading.

[figure not shown]
